### 8.4.2 Efficacy/Pharmacokinetics/Pharmacodynamics Endpoints

Secondary efficacy endpoints are presented below:

**Objective Response Rate (ORR):** is defined as the percentage of subjects who have achieved confirmed complete response (CR) or partial response (PR) according to specified response criteria for each tumor type (AML or DLBCL) by the investigator review.

**Duration of Response (DOR):** is defined as the time interval between the date of the first confirmed response (CR/PR) (the response prior to confirmation) and the date of first documented disease progression based upon specified response criteria for each tumor type (AML or DLBCL) by the investigator review.

**Disease Control Rate (DCR):** is defined as the percentage of subjects who have achieved stable disease or confirmed complete response (CR) or confirmed partial response (PR) according to Response Evaluation Criteria in AML or DLBCL (see Section 7.1.2.7.1 and 7.1.2.7.2) by the investigator review. Subjects with missing response will be considered not to have achieved disease control.

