#### 4.2.3.3 Efficacy Endpoints

##### 4.2.3.3.1 Secondary Efficacy Endpoints

The secondary efficacy objectives for this trial are to evaluate the anti-tumor activity of MK-8628 in subjects with AML (de Novo and post-MDS) and DLBCL biomarker unselected. Secondary efficacy endpoints include (1) ORR, defined per standard response criteria for acute leukemia (Section 12.4) and malignant lymphoma (Sections 12.5), as assessed by investigator, (2) DOR, defined as the time from first documented evidence of CR or PR until disease progression or death due to any cause, whichever occurs first, (3) disease control rate defined as the percentage of subjects with advanced or metastatic cancer who have achieved CR, PR and stable disease.

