#### 4.2.3.3.2 Exploratory Efficacy Endpoints

Exploratory efficacy endpoints include PFS, defined as the time from allocation to the first documented disease progression according to Response Evaluation Criteria in AML or DLBCL (see Section 7.1.2.7.1 and 7.1.2.7.2), or death due to any cause, whichever occurs first, and OS.

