##### 7.1.5.4.2 Additional Follow-up

In subjects who discontinue study therapy without documented disease progression, every effort should be made to continue monitoring their disease status every 6 weeks ( $\pm$  3 days) for AML subjects and every 12 weeks ( $\pm$  7 days) for DLBCL subjects until (1) the start of new anti-cancer treatment, (2) documented disease progression, (3) death, or (4) the end of the study, whichever occurs first. If subjects have stable disease, partial response, or complete response, they should continue on this assessment schedule. Tumor response assessments should occur at any time where there is clinical suspicion of progression or relapse.

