### 7.2.3 Immediate Reporting of Adverse Events to the Sponsor

#### 7.2.3.1 Serious Adverse Events

A serious adverse event is any adverse event occurring at any dose or during any use of Sponsor's product that:

- Results in death;
- Is life threatening;
- Results in persistent or significant disability/incapacity;
- Results in or prolongs an existing inpatient hospitalization;
- Is a congenital anomaly/birth defect;
- Is an other important medical event.

**Note:** In addition to the above criteria, adverse events meeting either of the below criteria, although not serious per ICH definition, are reportable to the Sponsor in the same timeframe as SAEs to meet certain local requirements. Therefore, these events are considered serious by the Sponsor for collection purposes.

- Is a new cancer (that is not a condition of the study);
- Is associated with an overdose.

Refer to [Table 10](#) for additional details regarding each of the above criteria.

For the time period beginning when the consent form is signed until treatment allocation/randomization, any serious adverse event, or follow up to a serious adverse event, including death due to any cause other than progression of the cancer under study (reference Section 7.2.3.3 for additional details), that occurs to any subject must be reported within 24 hours to the Sponsor if it causes the subject to be excluded from the trial, or is the result of a protocol-specified intervention, including but not limited to washout or discontinuation of usual therapy, diet, placebo treatment or a procedure.

For the time period beginning at treatment allocation/randomization through 30 days following cessation of treatment, any serious adverse event, or follow up to a serious adverse event, including death due to any cause other than progression of the cancer under study (reference Section 7.2.3.3 for additional details), whether or not related to the Sponsor's product, must be reported within 24 hours to the Sponsor either by electronic media or paper. Electronic reporting procedures can be found in the EDC data entry guidelines. Paper reporting procedures can be found in the Investigator Trial File Binder (or equivalent).

Additionally, any serious adverse event, considered by an investigator who is a qualified physician to be related to the Sponsor's product that is brought to the attention of the investigator at any time following consent through the end of the specified safety follow-up

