## 8.6 Statistical Methods

This section describes the statistical methods to address the primary and secondary objectives. Methods related to exploratory endpoints will be described in the supplemental SAP. Data will be presented by dose level and where appropriate by indication. No imputations for missing data will be made.

Pharmacokinetics and pharmacodynamics will be analyzed and reported separately.

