### 8.6.2 Statistical Methods for Efficacy Analyses

ORR and DCR will be estimated using an exact method based on binomial distribution (Clopper-Pearson interval) for each tumor type (AML or DLBCL).

DOR will be estimated by Kaplan-Meier method.

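### Duration of response ends at progression or death in Section 4.2.3.3.1 but at documented progression only in Section 8.4.2, and no event or censoring rule settles the conflict

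*Combined protocol and SAP*

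**What the plan says.** Section 4.2.3.3.1 defines DOR as "the time from first documented evidence of CR or PR until disease progression or death due to any cause, whichever occurs first". Section 8.4.2, the definition in the analysis plan, starts the interval at "the date of the first confirmed response (CR/PR) (the response prior to confirmation") and ends it at "the date of first documented disease progression based upon specified response criteria for each tumor type (AML or DLBCL) by the investigator review". Death does not appear there.

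The neighbouring endpoint follows the first pattern. Progression-free survival (PFS) in Section 4.2.3.3.2 ends at documented progression "or death due to any cause, whichever occurs first, and OS".

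On method, Section 8.6.2 says only "DOR will be estimated by Kaplan-Meier method". Section 8.6 adds "No imputations for missing data will be made" and defers methods for exploratory endpoints to the supplemental SAP. DOR is a secondary endpoint (Section 3.2), so that deferral does not cover it.

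Both definitions stand in the current body of the document. Neither comes from the summary of changes.

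**The concern.** A Kaplan-Meier analysis needs to know which outcomes are events and when everyone else is censored. Here the two definitions disagree on whether death is an event, and there is no censoring rule to fall back on. Two analysts, each following one section, could report different DOR results from the same data.

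If 8.4.2 is followed literally, a responder who dies before progression is documented never has an event. Censoring such a death assumes that the subject would have gone on with the same progression risk as the responders still under observation. For a death that ends a response, that is hard to defend. It also departs from the protocol's own definition in 4.2.3.3.1.

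What is at stake is how DOR is described from data already collected. Section 10.7 says the trial is intended for publication even if it stops early.

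**Working it through.** The plan gives no figure for DOR, so there is none to reproduce. The check is a comparison of text, followed by small examples with assumed times.

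**1. The definitions by outcome**

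| Responder's course | Section 4.2.3.3.1 | Section 8.4.2 |
|---|---|---|
| Progression documented first | Event at progression | Event at progression |
| Dies without documented progression | Event at death | No event; handling not stated |
| Alive without progression | No event; censoring date not stated | No event; censoring date not stated |

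Only the second row differs on the end event.

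**2. Search for a rule that settles it.** Section 8.6.2 names the method only. The statement in 8.6 on imputation is not a censoring rule. Section 7.1.5.4.2 says that, after treatment stops without progression, disease monitoring continues "until (1) the start of new anti-cancer treatment, (2) documented disease progression, (3) death, or (4) the end of the study, whichever occurs first". The flow chart notes and Sections 7.1.2.7.1 and 7.1.2.7.2 say the same. These are visit rules and do not say how DOR is analysed.

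**3. Start date.** Section 4.2.3.3.1 starts at the first documented response. Section 8.4.2 starts at the first response that is later confirmed, dated before the confirmation. The two coincide when the first documented response is the one confirmed. Where they differ for a subject, the 8.4.2 start is later. A responder who is never confirmed has no start date under 8.4.2.

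**4. Effect on the Kaplan-Meier estimate.** S(t) is the product of (1 − d/n) over event times, and the median is the first time S(t) is 1/2 or less. All times below are assumed.

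*Example A, death censored on the day it occurs.* Four responders have end times of 2, 3, 5 and 8 months, and the one at 3 months is a death.
- Death counted: S(2) = 3/4; S(3) = 3/4 × 2/3 = 1/2. Median 3 months.
- Death censored at 3: S(2) = 3/4; S(5) = 3/4 × 1/2 = 3/8. Median 5 months.

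*Example B, death censored at the last assessment.* X progresses at 4.5 months. Y dies at 5, last assessed at 4. Z progresses at 8.
- Death counted: S(4.5) = 2/3; S(5) = 2/3 × 1/2 = 1/3.
- Y censored at 4: S(4.5) = 1/2; S(5) = 1/2.

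The curves cross. Censoring gives the lower estimate at 4.5 months and the higher one at 5. Gaps of this kind are realistic, because DLBCL response is assessed every 12 weeks (Section 7.1.2.7.2).

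**5. Rough scale, by assumption only.** Suppose hazards are constant, the median time to progression or death is M, a share s of first end events are deaths without documented progression, and those deaths are censored when they occur. The estimated median then becomes M/(1 − s). With M assumed to be 5 months:
- s = 0: 5 months
- s = 10%: 5/0.9 = 5.6 months
- s = 20%: 5/0.8 = 6.25 months
- s = 30%: 5/0.7 = 7.1 months
- s = 50%: 5/0.5 = 10 months

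The documents give neither M nor s for this trial, so these values show only how the result depends on s.

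**The case against.** The strongest reply is that this has very little practical weight. Section 8.3 states that there are no hypotheses. Section 5.2.1.4 makes the DLT rate the driver of dose selection. Section 1.0 says enrollment has stopped, the database will close and no further efficacy measures will be recorded. All of this stands, and it fixes the severity. It does not remove the conflict, because DOR may still be reported from the responses already on file.

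A reader might infer that 8.4.2 must always give the longer DOR. For a common start date, that is true of the underlying time, since time to progression cannot be shorter than time to progression or death. It is not guaranteed for the reported Kaplan-Meier estimate, as Example B shows, and the documents give no censoring date. A reader might also take it as stated that deaths are censored. That is an inference from 8.4.2; no section says so.

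It is also tempting to size the problem from the response rates in MK-8628-001. Those rates would suggest how many responders to expect, at other doses and schedules. They say nothing about how many responders die without documented progression, which is what determines the effect.

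The definition of confirmation, the end event for an AML partial remission and the handling of new anticancer therapy are separate matters of missing detail or convention. They do not form part of this conflict.

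**Conclusion.** The conflict is real and minor. Two current sections define the same secondary endpoint differently on whether death is an event, and the methods section does not choose between them. As written, 8.4.2 leaves a responder who dies without documented progression with no end event, contrary to 4.2.3.3.1 and out of line with the PFS definition.

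The size cannot be computed from the documents. It is zero if no responder dies without documented progression. If some do, and if they are censored, reported DOR would generally tend to be longer, with no guaranteed direction at a given time point. The documents do not support any claim that this affects the recommended phase 2 dose or a confirmatory conclusion.

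**What to change.** - **Section 8.4.2:** end DOR at first documented progression or death from any cause, whichever comes first, to match 4.2.3.3.1 and the PFS definition. For an AML complete remission, name relapse as the progression event, because Table 13 has no progression category.
- **Sections 4.2.3.3.1 and 8.4.2:** use the same start date in both.
- **Section 8.6.2:** state that responders alive without progression are censored at their last disease assessment.

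Section 8.0 allows changes to non-confirmatory analyses to be recorded in the supplemental SAP before final database lock. If the database is already locked, the clinical study report should state the definition used.

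The cost is a few sentences and no new procedures. The downside is a possibly shorter reported DOR. Death is already a stopping point of disease follow-up, and through 30 days after treatment serious adverse event reporting covers events "including death due to any cause other than progression of the cancer under study" (Section 7.2.3.1). Deaths after follow-up ends, for example after new anticancer treatment starts, may not be known. That should be reported as a limitation.

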### Pharmacokinetics

Plasma parameters of MK-8628 as appropriate and according to analyses performed (non-compartmental or nonlinear mixed effect modelling).

### Pharmacodynamics

Incidence and severity of AEs along with PK parameters will be analyzed in relation to the most pertinent biomarker(s), if any.

## 8.5 Analysis Populations

### 8.5.1 Safety Analysis Populations

**DLT Evaluable population:** subjects who receive at least 85% of the planned dose of study drug (18 days) or experience DLT during the first 21-day cycle.

The **All Subjects as Treated (ASaT)** population, also known as **treated population**, consisting of subjects who receive at least one dose of study drug, will be used for the analysis of all other safety data in this study.

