#### 5.2.1.2 Dose Escalation

A twice daily (BID) dose escalation will be performed using a 6+8 two-stage design with continuous DLT rate monitoring via a modified toxicity probability index (mTPI) (Ji design), targeting a maximum 25% DLT rate [1].

Two planned dose levels will be evaluated sequentially: 20 mg BID and 30 mg BID (all continuous daily). See [Table 3](#) and [Table 4](#) for the dose escalation scheme.

Table 3 Dose Escalation Scheme

Dose Level (DL)	MK-8628 (mg/dose) BID Regimen (continuous)	Outcome (#DLT/#Subjects)* / Actions to be taken
DL 1	20	At each DL: - Escalate/de-escalate per DLT rate observed using mTPI (Table 4)
DL 2	30	

\* Evaluated during the first 21 days of treatment

Table 4 Modified Toxicity Probability Interval (mTPI) Design

Number of toxicities	Number of subjects treated at current dose								
	6	7	8	9	10	11	12	13	14
0	E	E	E	E	E	E	E	E	E
1	S	E	E	E	E	E	E	E	E
2	S	S	S	S	S	S	S	S	E
3	D	S	S	S	S	S	S	S	S
4	DU	DU	DU	D	S	S	S	S	S
5	DU	DU	DU	DU	DU	D	S	S	S
6	DU	DU	DU	DU	DU	DU	DU	DU	D
7		DU							
8			DU						
9				DU	DU	DU	DU	DU	DU
10					DU	DU	DU	DU	DU
11						DU	DU	DU	DU
12							DU	DU	DU
13								DU	DU
14									DU

E = Escalate to the next higher dose  
S = Stay at the current dose  
D = De-escalate to the next lower dose  
DU = The current dose is unacceptable  
Target toxicity rate = 25%

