**E = Escalate; S = Stay; D = De-escalate; DU = Unacceptable**

Note:

- De-escalation at lowest dose level indicates stopping of trial
- Escalation at highest dose level indicates staying at that level

Each cohort (AML and DLBCL) will be evaluated independently in regards to enrollment and dose level escalation/de-escalation.

Subjects may be enrolled continuously (i.e., without waiting for Cycle 1 completion of subjects who have received the first dose) unless a DLT is observed at the particular dose. If 0 out of the first 6 subjects in a given dose level develop a DLT, then the dose can escalate to the next level without further expansion. If 3 patients out of the first 6 patients develop a DLT, the dose will be de-escalated to the next lowest dose level. If  $\geq 4$  out of the first 6 patients develop a DLT, this indicates an unacceptable toxicity. If 1 to 2 out of the first 6 subjects of a given dose level develop a DLT, expand the current dose level according to [Table 4](#) by continuing enrollment as follows. The number of subjects who are enrolled at that dose but are not yet fully evaluable for DLT assessment may not exceed the number of remaining subjects who are at risk of developing a DLT before the dose would be considered unacceptably toxic (denoted as DU in [Table 4](#)). For example, if 2/7 subjects have experienced a DLT at a given dose level, no more than an additional 3 subjects should be enrolled at this dose level until additional DLT data are available. This is because this dose level would be considered unacceptably toxic if all 3 of the additional subjects experience a DLT (i.e., 5/10 subjects with DLT in [Table 4](#)). To find out how many more subjects can be enrolled, one can count steps in diagonal direction (down and to the right) from the cell (7 subjects, 2 toxicities) to the first cell marked DU.

De-escalation (D) or unacceptable (DU) at the lowest dose level (DL1) indicates stopping of the trial. Escalation (E) at the highest dose level (DL2) indicates staying at that level. Note that while 25% has been the target toxicity rate used to generate the guidelines in [Table 4](#), the observed rate of subjects with DLT at the RP2D may be slightly above or below 25%.

Subjects not evaluable for DLT (i.e. receiving less than 85% of the intended cumulative dose in Cycle 1 for any reason other than toxicity; < 18 days of treatment) and who do not experience DLT will be replaced.

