#### 5.2.1.3 Definition of Dose Limiting Toxicity

DLT is defined as any of the following toxicities occurring during the first cycle of treatment (21 days) for each dose level. See Section 5.9 for rules on replacement of subjects in the DLT period.

The occurrence of any of the following toxicities during Cycle 1, **if assessed by the investigator to be possibly, probably or definitely related to MK-8628**, will be considered a DLT:

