**Hematologic Toxicity:**

AML

1. Pancytopenia with a hypocellular bone marrow and no marrow blasts lasting for  $\geq 6$  weeks after the start of a cycle. For subjects with AML who have a suspected DLT in case of pancytopenia with a hypocellular bone marrow and no marrow blast on Day 22 bone marrow aspiration, the DLT window will be extended to the first 2 cycles or Day 42 for repeat bone marrow confirmation. However, enrollment of additional patients at this dose level should not be delayed during the extended window for DLT in this situation assuming a confirmed DLT for such a subject would not affect a dose escalation or de-escalation decision.

DLBCL

1. Grade 4 hematologic toxicity lasting  $\geq 7$  days, except thrombocytopenia  
Grade 4 thrombocytopenia of any duration  
Grade 3 thrombocytopenia is a DLT if associated with bleeding
2. Febrile or infection related neutropenia, Grade 3 or Grade 4

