**Other Toxicity:**

1. Any drug-related AE which caused subject to discontinue treatment during Cycle 1
2. Any study drug-related toxicity resulting in a subject missing  $\geq 20\%$  of planned doses during Cycle 1.
3. Any treatment-related toxicity which causes a greater than 2 week delay in initiation of Cycle 2.
4. Grade 5 toxicity

DLTs must be reported within 24 hours to the Sponsor as Events of Clinical Interest (see Section 7.2.3.2). If the event also meets the criteria for seriousness, follow the reporting guidelines for Serious Adverse Events (SAEs) outlined in Section 7.2.3.1.

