## **5.9 Subject Replacement Strategy**

Subjects not evaluable for DLT (i.e. receiving less than 85% of the intended cumulative dose in Cycle 1 for any reason other than toxicity; < 18 days of treatment) and who do not experience DLT will be replaced.

A subject who discontinues from the trial for any other reason will not be replaced.

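### Section 8.5.1's DLT-evaluable definition omits the toxicity exception of Sections 5.2.1.2 and 5.9, so a subject under-dosed for toxicity without a DLT is neither replaced nor counted in the primary DLT rate

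*Combined protocol and SAP*

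**What the plan says.** Section 8.5.1 defines the DLT Evaluable population as "subjects who receive at least 85% of the planned dose of study drug (18 days) or experience DLT during the first 21-day cycle". The reason for a shortfall plays no part. The same section assigns the all-treated population to the remaining safety data, so the DLT Evaluable set is the denominator of the primary endpoint, the proportion with at least one Cycle 1 DLT (Sections 8.1 and 8.4.1). That proportion is reported with an 80% credible interval under a Beta(1,1) prior (Section 8.6.1).

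Section 5.9 spells out who is not evaluable for DLT: those "receiving less than 85% of the intended cumulative dose in Cycle 1 for any reason other than toxicity; < 18 days of treatment". Section 5.2.1.2 uses the same rule, ending "for any reason other than toxicity; < 18 days of treatment) and who do not experience DLT will be replaced". Section 5.9 adds that subjects who leave for other reasons are not replaced.

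The columns of Table 4, which drives escalation, are headed "Number of subjects treated at current dose". Section 8.7 refers to subjects evaluable for DLT but does not say which definition applies.

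Two features of Section 5.2.1.3 set the limits of the gap. An event is a DLT only "if assessed by the investigator to be possibly, probably or definitely related to MK-8628". The list also includes "Any study drug-related toxicity resulting in a subject missing" 20% or more of the planned Cycle 1 doses, and drug-related discontinuation in Cycle 1.

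**The concern.** The two definitions treat one kind of subject differently: someone who received less than 85% because of toxicity but had no DLT. Under Sections 5.2.1.2 and 5.9 this subject is not among the non-evaluable and is not replaced. Under Section 8.5.1 the subject is outside the analysis set. The exclusion therefore depends on how the drug was tolerated, and it acts on the denominator of the primary estimate.

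Two things could follow, depending on what Section 8.7 means. If the ongoing assessments follow Section 5.2.1.2, the count behind the dose decisions and the count in the report can differ for the same dose level. If they follow Section 8.5.1, the two counts agree, but losing such a subject can change the Table 4 action. Only one of these can apply.

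**Working it through.** **1. Is the affected group empty?** Inputs: twice-daily dosing for 21 days (Section 5.2), hence 21 × 2 = 42 planned doses; the 85% threshold (Section 8.5.1); the 20% missed-dose DLT criterion (Section 5.2.1.3).

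- 85% of 42 is 35.7, so a subject needs 36 doses and fails with 7 or more missed.
- 20% of 42 is 8.4, so the missed-dose DLT needs 9 or more missed.

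| Doses missed | Received | Missed | At least 85%? | Missed-dose DLT if drug-related? |
|---|---|---|---|---|
| 6 | 85.7% | 14.3% | yes | no |
| 7 | 83.3% | 16.7% | no | no |
| 8 | 81.0% | 19.0% | no | no |
| 9 | 78.6% | 21.4% | no | yes |

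Seven or eight missed doses fall between the two rules. If the 18 days in Section 8.5.1 are instead counted as days with any dose, one block of 7 missed doses removes only 3 whole days and leaves 18. Eight missed over 4 whole days leaves 17 and fails on either count.

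**2. Can such a hold happen without a DLT?** Yes. Section 5.2.1.5 withholds drug for drug-related Grade 4 hematologic toxicity, whereas the only AML hematologic DLT is "Pancytopenia with a hypocellular bone marrow and no marrow blasts lasting for" six weeks or more. Table 5 also holds drug in DLBCL for Grade 3 thrombocytopenia lasting more than 7 days, which Section 5.2.1.3 counts as a DLT only with bleeding. To stay at 7 or 8 missed doses (3.5 or 4 days), the hold must resolve in about four days or begin in the last four days of the cycle.

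**3. Reproducing the plan's figures.** With x DLTs in n subjects the posterior is Beta(1 + x, 1 + n − x). The shortest interval holding 80% probability (HPD) for 3/14 is 0.102 to 0.367, as in Table 11. All 11 rows of that table reproduce this way. The equal-tailed interval for 3/14 is 0.122 to 0.393 and does not match.

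**4. Effect on the reported rate.** Removing k non-DLT subjects changes x/n to x/(n − k), which is never smaller. Assume 14 enrolled, 3 with a DLT and 1 affected subject:

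- Sections 5.2.1.2 and 5.9: 3/14 = 21.4%, 80% HPD 0.102 to 0.367.
- Section 8.5.1: 3/13 = 23.1%, 80% HPD 0.111 to 0.391.
- Difference: 3/13 − 3/14 = 3/182 = 1.6 percentage points.

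**5. Effect on Table 4 if Section 8.7 follows Section 8.5.1.** Lowering n by one at the same DLT count changes the printed action in eight cells, each time to a more cautious one:

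- E to S: 1/7, 2/14.
- S to D: 3/7, 4/10, 5/12.
- D to DU: 4/9, 5/11, 6/14.

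Section 5.2.1.2 says D and DU at the lowest level both stop the trial, so the three D-to-DU cells have no effect at DL1: 8 − 3 = 5 effective changes. It also says E at the highest level means staying, so the two E-to-S cells have no effect at DL2: 8 − 2 = 6 effective changes, three of them D to DU.

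**The case against.** The strongest reply is that the difference is mostly one of drafting. Sections 5.2.1.2 and 5.9 are replacement rules, and no sentence says outright that a subject under-dosed for toxicity stays in the decision count. That is inferred from how the two sections spell out non-evaluability and from the Table 4 column heading. Section 8.5.1 is the only population defined under that name, so Section 8.7 may well point to it. This stands as a caution. It does not remove the conflict, because a subject who is not among the non-evaluable in one section is excluded in another.

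Second, the DLT list already captures most drug-related under-dosing, through discontinuation and the 20% criterion. This is correct and makes the group narrow, but step 1 shows that it is not empty.

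Third, holding enrolment at 14 is an assumption. The cap is expressed in evaluable subjects (Sections 2.1, 8.1 and 8.9), so a subject outside Section 8.5.1 might not use up a place. This also stands.

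Fourth, the bias is conservative, no hypothesis is tested (Section 8.3), RP2D selection weighs several factors (Section 5.2.1.4), and enrolment has stopped (Section 1.0). For AML at 20 mg BID, decision and report counts already differ by design, because subjects from MK-8628-001 inform the decisions while this trial is analysed alone (Section 8.9). That difference is declared in the plan; this one is not.

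**Conclusion.** The inconsistency is real and minor. It rests on reading Sections 5.2.1.2 and 5.9 as defining evaluability, and on 85% being judged by doses received. The certain group is drug-related toxicity with 7 or 8 missed doses and no DLT. Its frequency is not given, so the 1.6-point shift for one subject in 14 is only an illustration. The direction is certain: the reported rate stays the same or rises.

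A reader might infer more than the documents support:

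- **That the rate would cross the 25% mark.** This would take, for example, two affected subjects at one dose level in one cohort (3/12 = 25.0%), for which there is no evidence. Section 5.2.1.2 itself accepts that "the observed rate of subjects with DLT at the RP2D may be slightly above or below 25" per cent.
- **That eight dose decisions are at risk.** At most five actions change in effect at DL1 and six at DL2, and only if Section 8.7 follows Section 8.5.1. In that case the mismatch between decision and report disappears.
- **That in-cycle dose reduction, or toxicity judged unrelated to drug, shows a further fault in Section 8.5.1.** The first turns on whether 85% means cumulative dose or 18 treated days, an ambiguity shared by all three sections. The second turns on whether toxicity in Sections 5.2.1.2 and 5.9 is limited to drug-related events, which is not stated. Both need clarifying but are secondary.

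**What to change.** Reconcile Sections 5.2.1.2, 5.9, 8.5.1 and 8.7 to one DLT-evaluable definition. Add to Section 8.5.1 a third route into the population, *or received <85% because of toxicity*, to match Sections 5.2.1.2 and 5.9, and have Section 8.7 refer to it. In the same edit, state whether toxicity is limited to drug-related events, and whether 85% is judged on cumulative dose or on 18 treated days. Report the DLT rate under the current Section 8.5.1 wording in a row beside the main one.

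Removing the toxicity exception from Sections 5.2.1.2 and 5.9 would also make the sections agree, but it would keep a tolerance-related exclusion in the primary denominator.

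The cost is one clause, one cross-reference, two clarifications and one extra table row. It needs no new subjects, procedures or data, and no dose or clinical rule changes. The downside is that incompletely exposed subjects count as non-DLTs, which slightly lowers the reported rate; the side-by-side row shows by how much.
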